The standard care for the control arm will be: the LACDHS Vaccine Hesitancy Outreach Group calling patients once every month to remind patients of the need to be vaccinated and tested if needed. During the duration of the six weeks, the study participants will be exposed to the call from the LACDHS Vaccine Hesitancy Outreach Group.

Participants will receive two phone calls six-weeks apart, where they will complete a pre-survey in the first phone call, and 2 surveys (post-survey and CDE survey) in the second phone call. The survey will measure their trust in medical institutions, rate their self-efficacy, and intention, knowledge, and perceptions on COVID-19 testing and vaccination. Each survey will take about a half hour to complete, with the total time commitment for participants in Group 1 is about 1-1.5 hours. A copy of the surveys will be sent to the study participant either by email (preferred) or postal mail, prior to the telephone call.

An outline of the activities in Group 1 will look like:

1. Complete the pre- survey
2. Wait 6 weeks, where the LACDHS Vaccine Outreach Group will call one time in the month to remind them about getting the vaccine
3. After the 6 weeks have passed, the study staff will follow up with the participant to complete the post-survey and the CDE survey.

Study staff will use the REDCap Calendar feature to track events (such as when to administer the pre- and post- surveys) and will be used for data entry. The filters and reminders on the calendar feature assist study staff with adding events to adhere to study follow up times for study staff to call participants six-weeks later. If participants do not answer the phone calls to complete the post-survey, we will add a note on the patient’s chart, follow up three times to provide additional opportunities for patients to complete the study, and mark the patient’s chart as “Incomplete”. Once phone calls and post- surveys are complete, study staff will mark the participants’ charts as “Complete.”

Intervention Arm - CHW-led curriculum (Group 2)

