Once the project is completed, both groups will be asked to complete a Common Data Element Survey as requested by the NIH's terms and conditions. A priority of the RADx initiative is to build the RADx Data Hub, the NIH's resources of RADx-generated research data that can help other researchers and public health officials better understand the impact of the COVID-19 pandemic, including outcomes, disparities, and possible solutions. RADx-UP projects collect data for the RADx Data Hub and simplify the analysis of that data, the NIH defined a set of Common Data Elements (CDEs). The NIH RADx-UP CDEs provide a standard set of study questions that RADx-UP projects are required to use in their COVID-19 studies. Additional information can be found at <https://radx-up.org/learning-resources/cdes/>

9. Surveys, questionnaires, or psychological tests: If your study uses surveys, questionnaires, or psychological tests, please list and describe the setting, mode of administration, the length of administration time, number of repeats, and if special training or qualifications are necessary to administer the study instruments. Describe provisions for maintaining privacy and confidentiality.

All the following surveys and questionnaires will be comprehensible to participants by ensuring readability checks on the type of language used, simplicity of language, and additional explanation of concepts.

A basic demographic survey (**see attached: Basic Demographic Survey**) will be administered on a phone call when the patient has been consented and enrolled in the study. In this demographic survey, the survey consists of demographic questions such as age, race and ethnicity, education level, and other sociodemographic questions and will take about 10 minutes to complete.

Pre- and post- surveys (**see attached: Pre- and Post- RADxUP Survey**) will be administered telephonically by study staff to enrolled study participants. These surveys will be provided to both control and case arms, to measure three key measures: trust, self-efficacy,

and intent to participate in COVID-19 testing and vaccination. Secondary measures included will use brief measures from the RADxUP and Phenx database of COVID protocols such as worry about COVID-19, knowledge, attitudes, behaviors, social support, perceived COVID-19 threat, and sources of information about COVID-19.

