- **Pre- surveys** will be administered by IRB-approved study staff, after study participants are consented and enrolled into the study and at a convenient time for the study participant. The survey should take about 30-60 minutes to complete (**see Pre- and Post- RADxUP Survey**). The survey questions and answers will be sent via email or mail prior to the phone call, and read and answered over the phone by the study staff to overcome any misinterpretation of the survey questions. The participant's response will be input by the study staff directly into REDCap under the subject ID#. No special training will be required to administer the survey.
- **Post- surveys** will take between 30-60 minutes to complete (**see Pre- and Post- RADxUP Survey**). The survey questions and answers will be read and answered over the phone by study staff to overcome any misinterpretation of the survey questions. The participant's response will be input by the study staff directly into REDCap under the subject ID#. No special training will be required to administer the survey.
 - o The post survey will be administered by study staff telephonically (similar to the pre-survey process) after:
 - Control arm – 6 weeks from the first survey
 - Case arm – after they complete the 6th group class and 6th personal phone call with the CHW

As part of the intervention arm, the modules will incorporate weekly formal “Knowledge Checks” (**see Knowledge Checks**) a comprehension questionnaire administered via email survey (sent by REDCap) sent after each module, which all participants will complete before their personal phone call with the CHW. The purpose of these Knowledge Checks is for the study team to measure patients' comprehension after each group session and throughout the course of the study. If patients score low in the Knowledge Checks, the CHW will review with the patients during their personal sessions to increase comprehension of the materials presented during the group session. There will be a total of 5 Knowledge Checks for Modules 1-5 (the Post- survey will be administered in lieu of a Knowledge Check for Module 6), each with 5-10 multiple-choice questions.

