Post- survey – like the pre- survey, the post- survey will be administered telephonically with study staff, at a time that is convenient for the study participant. The study staff, who are IRB approved, will resend the survey out before the phone call to read the questions and answer choices aloud and input the participant's answer directly into REDCap under the Subject ID#. Participants enrolled in both control and case arm will complete this survey. Participants in the control arm will complete the post- survey 6 weeks after they complete the pre- survey. Participants in the case arm will complete the survey after they attend the 6th group class and 6th phone call with the CHW.

Knowledge checks – this survey will only be administered to study participants randomly assigned to the case arm on a weekly basis, after they attend a group session. The survey will be sent out via email using the REDCap survey feature. If participants are not able to complete the survey via email, study staff will follow up with the participants via phone call to complete the survey where study staff will read the questions and answers aloud. The

study staff will then enter the answers directly into REDCap. This survey will need to be completed before the participants complete their personal phone calls with the CHW.

Patient encounter forms – this data collection tool will only be used on study participants randomly assigned to the case arm during their weekly teleconsultations. Intervention CHWs will complete these forms after each of their teleconsultations (personal phone calls) with their assigned study participants and enter their notes on REDCap. Each participant will have six completed patient encounter forms in their subject file on REDCap by the end of the study. The teleconsultations will be scheduled at a time that is convenient for both the participants and the CHWs.

One of the MPI and software programmer will strip personally identifiable information from the clinic data and substitute with a random code (Subject ID#). A master code list will be created separately that will link the code with the patient. This master code list will reside in a separate file in REDCap.

b. Where will the data be stored and how will it be secured during the study?

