The potential benefits of the research must justify the risks to research participants. The risk/benefit ratio of the research must be at least as favorable for the participants as that presented by standard treatments for their condition. When comparing the risk/benefit ratio of research with that of available alternatives, the alternative of doing nothing should be included in the analysis.

The risk/benefit ratio of this research is favorable, because this is a low risk study and we aim to minimize the risk in several ways, (e.g. limiting who has access to the data, the use of REDCap to collect data, the use of unique study ID# on the participant's data and keeping the master code list in a separate, secure location). While there is no direct benefit to the individual participant, there may be a benefit to society in that the information gained in the study. Findings from this study may help identify barriers to COVID 19 testing, vaccination, and health care for African American and Latino patients in the Los Angeles County Department of Health Services, which may also inform the challenges faced by African American and Latino patients in similar County health care systems in other cities. The risks to the participants are reasonable in relation to the importance of knowledge to be gained.

Financial Considerations

17. Payment for Participation: Describe all plans to compensate participants, including provision of services, and other reimbursements. Describe the conditions that participants must fulfill to receive full or partial payment.

Study participants in the case arm will receive a \$599 compensation (71 participants), and study participants in the control arm will receive \$100 compensation (71 participants) for their time and effort.

Control arm:

Participants in the control arm will be compensated with a \$100 gift card at the end of the study, after they complete the basic demographic, CDE, pre- and post- surveys. If the participant starts the surveys and cannot complete the required pre-, post-, and demographic surveys, then the participant will get the partial payment of \$50.

Case arm:

Participants will be compensated in weekly installments, after completing the first week of the 6-week program, the participant will receive a \$99 gift card, and subsequent weeks with \$100 gift cards for every successful week of completion (group session and personal session with CHW).

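### The post-survey is due on a calendar date in controls but on reaching the 6th class and 6th call in the intervention arm, so intervention patients who do not get that far have no survey date

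*Protocol*

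**What the plan says.** The Protocol's item on surveys (Section VI, item 9) gives both arms a pre- and a post-survey "to measure three key measures: trust, self-efficacy" and intent to take part in testing and vaccination. It then times the post-survey differently by arm. Controls are due "6 weeks from the first survey". The intervention arm, which the Protocol also calls the case arm, is due "after they complete the 6th group class and 6th personal phone call with the CHW".

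The data collection item (item 10) repeats this: "Participants in the case arm will complete the survey after they attend the 6th group class and 6th phone call with the CHW". The same paragraph says "Participants enrolled in both control and case arm will complete this survey".

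Other provisions bear on who is reached:

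- **Contact attempts.** Under the control arm in item 8, staff use calendar reminders. If a patient does not answer the post-survey call, they "follow up three times to provide additional opportunities for patients to complete the study". The intervention-arm text has no such rule.
- **Payment (item 17).** Controls receive the full 100 dollars "after they complete the basic demographic, CDE, pre- and post- surveys", or 50 dollars if they start but cannot finish. Intervention patients are paid week by week for attending the class and the personal session. They get 50 dollars for an incomplete week and nothing further after dropout.
- **Start of classes.** Item 8 starts classes once a group of 5 to 8 has formed, with staggered starts. Item 10 requires only that the intervention pre-survey come before the classes and calls.

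**The concern.** One arm's outcome is triggered by a date. The other arm's is triggered by an attendance event that happens after randomisation and exists in that arm only. If staff follow the trigger as written, controls are surveyed whatever they did in the six weeks, while intervention patients are surveyed only if they stayed to the last class and call. The surveyed intervention patients would then be selected on engagement and the surveyed controls would not. Randomisation does not protect that comparison. All three key measures come from this one survey, so all three would be affected together.

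**Working it through.** **1. The plan's own figures.** The sample-size statement (item 25) reproduces. With 64 per arm, a 0.5 SD difference and a two-sided 5% t-test, the noncentrality is 0.5 / √(1/64 + 1/64) = 2.83 and power is 0.801, against the stated 80%. The intervention payment also reproduces: 99 + 5 × 100 = 599 dollars, the stated total. The weekly instalments therefore use up the whole sum and leave nothing tied to the post-survey. The point does not rest on an arithmetic error.

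**2. The two arms side by side.**

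| | Control | Intervention |
|---|---|---|
| Post-survey due | 6 weeks after pre-survey | After 6th class and 6th call |
| Date if sessions are not reached | Not applicable | None stated |
| Repeat contact attempts | Three | None stated |
| Payment tied to post-survey | Full 100 dollars (50 if started but not finished) | None of the 599 dollars |

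**3. Three kinds of intervention patient.**

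- Attends everything: has a trigger.
- Misses an earlier week but attends the 6th class and call: still has a trigger.
- Stops, is stopped, or otherwise does not reach the 6th sessions: has no trigger. Item 17 foresees such patients (incomplete weeks, a decision by study personnel, dropout) but settles only their payment.

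The gap is confined to the third kind.

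**4. What can be said about size.** Let f be the share of intervention patients in the third group. If f = 0 there is no effect. If f > 0, any bias depends on f, on how those patients' outcomes differ from the others', and on loss among controls. The Protocol gives none of these separately, only an allowance of about 10% attrition in each group. Neither size nor sign can be computed.

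**5. Imputation.** Item 25 imputes if 10% or more of the data are missing. On the literal rule, no intervention patient who failed to reach the 6th sessions would have a post-survey. Imputed values for them would have to come from patients who did reach the sessions or from controls. The data could not show whether that is reasonable.

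**6. Elapsed time.** The control interval is 6 weeks. The intervention interval is about w + 6 weeks, where w is the wait between pre-survey and first class. With w = 0 the intervals match, and each week of waiting adds a week. No limit on w is stated.

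**7. Programme length.** The recruitment script (item 7) and the intervention-arm text (item 8) give six weeks. The Intervention Design text in item 8 speaks of a 2-month intervention, about 2 × 52/12 = 8.7 weeks. A survey keyed to the programme's end needs one length.

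**The case against.** The best reply is that the trigger states a sequence and not who is eligible. Items 9 and 10 direct the survey to enrolled patients in both arms, and the recruitment script gives Group 2 its programme on top of the Group 1 surveys. Item 10 expects six completed encounter forms per intervention patient, so the 6th call is planned for everyone. A missed week does not end participation, class recordings are available to absentees, and the time commitment in item 8 places two half-hour phone calls within the six weeks.

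Much of this stands. The intent is plainly to survey everyone, and a reader who infers that the Protocol excludes non-completers goes too far, because nothing says so. But none of these texts gives a date or contact rule for a patient who does not reach the last sessions, and the operative trigger points the other way.

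Other inferences also go too far:

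- **A definite bias.** A figure in SD units would need assumed loss rates and outcome gaps. It would also have to allow for the planned analysis of change, covariate adjustment and imputation.
- **A broken recruitment target.** The allowance for attrition covers loss from any cause in either arm and is not an effect of this rule.
- **Further contradictions.** Using the post-survey in place of the sixth Knowledge Check explains why there are only five checks. It does not clearly move the survey ahead of the call. The two months in the text on recruiting community health workers describes their workload over implementation, which staggered groups can explain.

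**Conclusion.** The concern holds as a gap in outcome collection and should be fixed before data collection. The post-survey trigger differs in kind between arms, a foreseen group of intervention patients has no survey date, and the contact attempts cover controls only. Followed literally, loss of all three key measures would depend on engagement in one arm. This rests on staff following the stated trigger; if they call everyone regardless, the selection problem does not arise. A longer pre-to-post interval in the intervention arm is possible but conditional on a wait between the pre-survey and the first class.

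**What to change.** In the post-survey text of items 9 and 10, state that the post-survey is attempted in every randomised patient regardless of attendance, unless the patient declines contact. In the intervention arm, key it to the scheduled end of the group's six-week programme and not to sessions completed. Give both arms the same stated window and the same three contact attempts, and extend the calendar reminders in item 8 to both arms. Record the pre-to-post interval for each patient. Reconcile the 2-month wording under Intervention Design with the six-week programme.

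Leave the pre-survey where it is. It follows randomisation, so holding it back until a group forms would risk losing baselines in the intervention arm only.

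The cost is wording, calendar entries and calls to patients who do not reach the 6th sessions. If all of the planned attrition of about 10% among the 71 intervention patients were of this kind (an assumption), that is 0.10 × 71 ≈ 7 patients. Instruments and control timing do not change.

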The study team will administer the **Common Data Elements (CDE) Survey** as provided by the funding partner, RADxUP (**see RADxUP CDE Survey attached**), the survey will be sent via email at the end of the project. Participants will be asked to complete it once. The survey can take up for 45minutes to an hour, no special training is required. In the RADxUP website, the reason for collecting the CDE's is "... to ensure consistency in how RADx-UP projects collect data for the RADx Data Hub and simplify the analysis of that data, the NIH defined a set of Common Data Elements (CDEs). The NIH RADx-UP CDEs provide a standard set of study questions that RADx-UP projects are required to use in their COVID-19 testing studies." More information can be found at <https://radx-up.org/learning-resources/cdes/>

10. Data Collection, Storage and Confidentiality: Please complete the following questions regarding data.

- a. How will the data be collected and recorded? How will the data be coded to protect personal privacy?

Data Collection:

The different types of data that will be collected in this aim are:

- Verbal Consents
- Basic Demographic Survey
- CDE survey (NIH's required survey)

- Pre- and post- surveys
- Knowledge Checks (comprehension questionnaires for intervention arm)
- Patient Encounter Forms (CHW reports for personal encounters in intervention arm)

Verbal consents – will be obtained telephonically by study staff before participants are enrolled in the study, and will be reviewed, recorded, and collected at a time that is convenient for the study participant. The study staff, who are IRB approved, will save the audio recordings on REDCap under the subject ID# with a date and time stamp, documenting when the participant provided their verbal consent.

Basic Demographic Survey – The survey will be administered and obtained telephonically with study staff at the end of the study, and will be reviewed and collected at a time that is convenient for the study participant. The answers to the survey will be input directly into REDCap under the subject ID# with a date and time stamp, documenting when the participant completed the survey.

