The data from Aim 3 will be stored in REDCap electronic data capture resource administered by the Biomedical Informatics Core function of AXIS (Accelerating Excellence in Translational Research) and the UCLA Clinical and Translational Science Institute (CTSI). REDCap (Research Electronic Data Capture) is a secure, web-based application designed to support data capture for research studies, providing: (1) an intuitive interface for validated data entry; (2) audit trails for tracking data manipulation and export procedures; (3) automated export procedures for seamless data downloads to common statistical packages; and (4) procedures for importing data from external sources.

CDU's REDCap servers are hosted by the University of California, San Diego Supercomputer Center. Vanderbilt University, with collaboration from a consortium of institutional partners, developed REDCap specifically around HIPAA-Security guidelines. REDCap can be used to easily build and manage online surveys and databases and all web-based information transmission is encrypted. REDCap currently has over 4641 collaborating institution in 139 countries wide with over 1.5 million end-users conducting 1 million projects (www.project-redcap.org). CDU's implementation of REDCap can be found at <https://redcap.cdrewu.edu>.

¹Paul A. Harris, Robert Taylor, Robert Thielke, Jonathon Payne, Nathaniel Gonzalez, Jose G. Conde, Research electronic data capture (REDCap) – A metadata-driven methodology and workflow process for providing translational research informatics support, J. Biomed Inform, 2009 Apr; 42(2):377-81.

c. Who will have access to the data and/or the data codes? If data with participant identifiers will be released, specify the person(s) or agencies to whom this information will be released.

The core study team (the MPIs, Machine Learning Specialist, Study Coordinator, and Research Assistant) will have access to the data and the data codes. The Biostatistician will have access to the data for data analysis, but not the data codes.

We will not release data with participant identifiers.

d. What will happen to the data when the study is completed? How long will the data be kept and what kind of identifiers will be associated with the data for long-term storage?

The data will be stored in REDCap for continued analysis and publication of manuscripts for up to six years after the overall study has been completed. During the six years, the coded link

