interviews, which ask about their attitudes towards COVID-19 testing and vaccination. However, the interviewers, who will be study staff, will have the training to respond to such discomfort and provide respondents with the option to not answer a question. If participants do become upset, they will have the option to stop their participation. They also can stop answering any question that makes them feel uncomfortable.

We will make every effort to prevent unauthorized access to patient identifying information by using a secure password protected computer and limiting the number of study personnel who can access the list. Whenever possible and particularly once all data collection is complete, we will use participants' unique study ID code, so that they are de-identified for data analysis. All study staff, including CHWs and all those with any contact with study participants or with collected data will have met all ethics certification requirements of the CDU IRB and have received training in how to ensure confidentiality and privacy of study participants and any identifiable data.

For Aim 3, all data collected on the patients will be stripped of confidential identifying information (e.g., name, medical record number, address, etc.) that could directly connect it back to a particular patient. However, each patient will be assigned a unique study ID code that allows us to link the data back to a particular patient, so that during data cleaning, we can check for additional information. A separate file linking unique identifiers and information about a patient will be created, and stored securely in CDU's instance of REDCap. Only the MPI overseeing this aim, Project Coordinator, and Machine Learning Specialist will have access to this master code list with the linking unique identifiers.

Additional safeguards includes having a regular meetings with the study team to review subject safety and data integrity, data security plan, implementing DSMP (see attached), keeping close communication with the participants, and resolving adverse events in a timely manner.

14. Potential Benefits to Participants and Society: Describe the potential benefits to the participants by being in the research and the potential benefits that the society might expect from this study.

Aim 3

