
2. Once the study staff confirms the study participants (or study participants' parents) have received and reviewed the consent form, we will answer any questions they might have and as a walkthrough of the consent form with them over the telephone. Study staff will also conduct a teach-back to ensure comprehension. After the teach back method, study staff will ask the participant to record the participants' consent to which we will ask them to state their name and agree to consent to being recorded for the following: initial recording of the consenting phone call, agreeing to being recorded during the group classes in Group 2 program (if assigned to the intervention arm), and to agree being enrolled in the study. The audio of the consent will be saved in REDCap as proof of consent.
 
a. On the consent form, it will only provide that they agree to being recorded if assigned to Group 2. The recordings will be done via Zoom and the Zoom recording feature automatically disconnects participants from the meeting if they do not agree to being recorded. By design, participants cannot disagree with being recorded because if they are randomly assigned to Group 2 and do not agree with being recorded, they will not be able to participant in the group meetings via Zoom. The Zoom recordings will serve as a back-up to ensure participants are able to review the class if they find themselves unable to attend the group class with the CHW.
 
3. For minors, consent/assent will be reaffirmed when the interviewer calls the participants after obtaining parental consent. The study staff will review the assent form with the minor participants and to obtain assent, the study staff will also ask the participant to be recorded for the following items: assent phone call, they agree to being recorded during the study, and consent to being enrolled in the study. The audio of the consent will be saved in REDCap as proof of consent.

b. When the consent is solicited (e.g., in relation to stressful events, hospital admission, surgery)

The consent will be solicited at a time of convenience to the potential participants

c. Opportunities for the potential participants to discuss their participation with family or others before signing the consent form

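### The consent audio, with the participant's spoken name, is filed under the coded subject ID, making a second link between code and person outside the restricted master list

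*Protocol*

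**What the plan says.** **Filing of the audio.** Item 10a of section VI lists verbal consents among the types of Aim 3 data. Staff are to "save the audio recordings on REDCap under the subject ID# with a date and time stamp". Surveys are entered under the same ID, and the community health workers' (CHWs') encounter forms go into the same subject file.

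**Content of the audio.** Item 22a describes the call with the participant or, for a minor, the parent: "we will ask them to state their name and agree to consent to being recorded for the following". It adds: "The audio of the consent will be saved in REDCap as proof of consent".

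**The stated separation.** Item 10a says: "A master code list will be created separately that will link the code with the patient". Item 13 says that for Aim 3 "all data collected on the patients will be stripped of confidential identifying information (e.g., name, medical record number, address, etc". On the link itself it says: "Only the MPI overseeing this aim, Project Coordinator, and Machine Learning Specialist will have access to this master code list".

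**Who holds the codes.** Item 10c gives both data and codes to the core team: the MPIs, the Machine Learning Specialist, the Study Coordinator and the Research Assistant. It then says: "The Biostatistician will have access to the data for data analysis, but not the data codes".

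**Why the separation is there.** Item 14 names breach of confidentiality, together with discomfort or anxiety, as the principal risk. Items 14 and 16 list the study ID and the separately kept master list among the measures that reduce it.

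**The concern.** Coding protects a participant only if the route from code to person runs through a file that few people can open. A recording in which the person says their name, indexed by the code, is another such route. Whoever can open that recording does not need the master list.

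At stake is a participant-protection property that the protocol claims and then relies on in its risk/benefit argument. The coded record holds answers on trust in medical institutions, and the Common Data Elements survey includes some questions that item 10a itself calls sensitive. The point has no bearing on sample size, randomisation or the analysis of outcomes.

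**Working it through.** No arithmetic applies. The check sets the statements side by side.

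1. **Does the audio carry a name?** Yes, for the consent step. Item 22a asks for the name as part of what is recorded. For a minor, the parent goes through this step. The separate assent step lists what the minor agrees to have recorded but does not mention a name.

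2. **Is the audio inside the coded record?** Yes. Item 10a files it under the subject ID. Item 22e agrees in substance: the recorded decision goes into the study file with date and time.

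3. **Is the audio covered by the promise to strip names?** As written, yes. Item 13 speaks of all data collected on patients in Aim 3, and item 10a counts verbal consents as Aim 3 data. The only stripping step that item 10a describes is for the clinic data. No step removes the name from the audio, and none could without spoiling it as proof of consent.

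4. **Is the audio given its own location or access rule?** No. Nothing in the protocol places it with the master list or states separate rights for it.

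5. **Result for the audio.** Steps 1 to 4 give a code-to-person link outside the master list. That contradicts the name-free data and the restricted link in item 13, and the separate link file in item 10a.

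6. **Do the two access lists agree?**

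| Role | Codes under item 10c | Master list under item 13 |
|---|---|---|
| MPI overseeing the aim | yes | yes |
| Other MPIs | yes | no |
| Study or Project Coordinator (taken as one role) | yes | yes |
| Machine Learning Specialist | yes | yes |
| Research Assistant | yes | no |
| Biostatistician | no | no |

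The lists differ on the other MPIs and the Research Assistant. The word used in item 13 is exclusive, so this is a contradiction. It does not depend on the audio. The data codes in item 10c are best read as the link to the person. If they meant only the subject ID, barring the Biostatistician from them would sit badly with the planned paired pre/post comparisons.

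7. **Who gains access through the audio?** Study staff make the recordings and telephone participants, so they know the names already. Intervention CHWs know their own assigned patients. That leaves anyone with record-level REDCap access who is not meant to hold the codes. The Biostatistician is the clearest example, and only if given records instead of a de-identified export.

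**The case against.** The strongest reply is that this is a narrow filing matter. With a waiver of documentation requested (item 22e), the recording is the proof of consent and must be traceable to a participant. An index by subject ID does not mean that every REDCap user can open the file. Item 13 intends data to be de-identified for analysis, item 10c bars release of identified data, and item 10d provides for de-identified sharing with the funder's programme. REDCap supplies audit trails and encryption. User rights may be set out in the attached data safety monitoring plan or the data security plan, which are not at hand.

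Most of this stands as a limit on the consequence. It does not reconcile the text. The audio can be traceable without sitting in the coded record, and an unseen attachment would not make items 10a and 22a agree with item 13.

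A reader might also infer more than the protocol supports:

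- **That the confidentiality protection is defeated.** One safeguard among several is weakened; the others listed above are untouched.
- **That participants are promised the opposite.** The consent form is not available, and the protocol does not report what it says about coding.
- **That CHWs could read named survey answers.** The protocol has CHWs write encounter forms and review material after low Knowledge Check scores. It does not give them the pre/post surveys, the Common Data Elements survey or the audio.
- **That the audio is why records stay identifiable for up to six years.** Item 10d keeps the coded link and the master list for that period anyway.
- **That each minor's own name is on tape.** The assent step does not say so.

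**Conclusion.** The contradiction is real and needs no assumption about REDCap: a recording with a spoken name, filed under the subject ID, cannot coexist with name-free data and a link open to three roles only. The conflict between items 10c and 13 over who holds the link is a separate error.

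The filing rule applies to the consent recording of every enrolled participant (planned recruitment 142), with the parent's name for minors. The consequence is modest. One of several safeguards against breach of confidentiality is undermined, and the added exposure falls only on people with record-level access who should not hold the codes. How many such people there are depends on REDCap user rights that the protocol does not state. The point is worth correcting because the protocol counts this separation among its safety precautions and the correction is nearly free.

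**What to change.** - In items 10a and 22a, store the consent and assent audio with the master code list, under the same restricted access. Leave only a consent date and time flag in the coded subject record.
- Replace the two statements in items 10c and 13 with one list of roles that may open the link, and use it in both places.
- State in item 10c that the Biostatistician works from a de-identified export, or that their record access excludes the audio.

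The cost is a few protocol sentences and minor REDCap set-up. Recruitment and analysis do not change. It is best done before the first consent is recorded; any audio already filed would have to be moved.
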